## F. Handling of Data Windows:

For visit-based assessments, a data point will be attributed to an analysis time point according to the nominal visit entered on the CRF. In phase I and II, visits are allowed to occur within 4 days of the expected visit date. In phase III, visits should occur within 7 days of the expected date. If many visits occur outside these windows, a sensitivity analysis will be conducted to assess if there is an impact of visits occurring outside of the window.

## G. Definition and Distribution of Age Brackets:

All sites are expected to recruit an evenly distributed proportion of patients across three defined age brackets, age 12 to 14, age 15 to 17, and age 18 to 21. Patient accrual will be actively monitored across these age brackets as the study progresses, and sites will be restricted from further recruitment within an age bracket if there is an imbalance in the distribution from that expected.

## Section 4. Population Demographic and Clinical Characteristics at Study Entry

As noted above, for all variables, data tables will be separately provided for the intent-to-treat and the perprotocol study populations. Unless otherwise stated, the primary and secondary outcomes of this study will be based upon analysis of the intent-to-treat study population observations, and the per-protocol study population will serve as a supporting analysis.

## A. Demographic and Clinical Variables:

The following demographic variables will be described for both study populations (Table 1).

Variable Name	Туре	Items
Gender	Categorical	Male
		Female
		Percentage
Age	Categorical by	Age year, Percentage
	year at entry	Grouped by 12-14, 15-17, 18-21
Ethnicity	Categorical	Hispanic or Latino
2	earegenear	Not Hispanic or Latino
		• Not Inspane of Launo
		Percentage
Race	Categorical	• White
		Black / African American
		• Asian
		American Indian or Alaska Native
		Native Hawaiian or other Pacific Islander
		• Other
		Percentage

|--|

## **B.** Illness Descriptive Variables:

The following illness descriptive variables will be described for both study populations at entry at phase I and will be described for each group for subjects entering Phases II and III (Table 2).

Table 2. Illness Descriptive Variables

Variable Name	Туре	Items
Primary Psychiatric Diagnosis	Categorical	Diagnosis Codes and Descriptions
Secondary Psychiatric Diagnoses	Categorical	Diagnosis Codes and Descriptions
		Note: For purposes of statistical analysis, secondary diagnoses should be dichotomized as None/Any Secondary Diagnosis
Prior Treatment History		
Prior ECT Treatment	Categorical	Yes/No

 
Prior Inpatient Hospitalization for Major Depression
 
	Categorical	Yes/No
• Prior Psychotherapy	Categorical	Yes/No
Prior Mania/Hypomania by YMRS	Categorical	Symptoms at entry of phase I
Baseline Symptom Severity		
HAMD24 Total Score	Continuous	Mean, SD, Median, Range
• HAMD17 Total Score (subset from HAMD24)	Continuous	Mean, SD, Median, Range
MADRS Item Total Score	Continuous	Mean, SD, Median, Range
CDRS-R Total Score	Continuous	Mean, SD, Median, Range
CGI-Severity of Illness Total	Continuous	Mean, SD, Median, Range

Score

QIDS-A17-SR

	Continuous	Mean, SD, Median, Range

The following variables will be used to describe pre-treatment psychiatric medication treatment history (Table 3). For the Antidepressant Treatment Record (ATR) medications, a listing will be provided showing the medications by class

## C. Psychiatric Medication History:

Table 3. Psychiatric Medication History

Variable Name	Туре	Items

 
Antidepressant Treatment Record
 
ATR-verified adequate antidepressant treatments
 
ATR-verified inadequate antidepressant treatments
 
	Continuous Categorical Continuous Categorical	Mean, SD, Median, Range Histogram of distribution of ATR categories Mean, SD, Median, Range Histogram of distribution # of antidepressant treatments not meeting ATR adequacy criteria
Other Psychiatric Medications	Categorical	Listing of medications used
Other Non-Psychiatric Medications	Categorical	Listing of medications used

## Section 5. Summary of Patient Disposition

#### A. CONSORT Diagram

Patient disposition (i.e., number of patients achieving a particular critical study stage) should be displayed for all consented patients in CONSORT diagram manner. At each study stage, the reasons for discontinuation up to and including that study time point should be listed. Each Phase of the study should have its own separate CONSORT diagram documenting patient disposition through that study Phase.

#### **B.** Reasons for Discontinuation

All enrolled patients should have a disposition recorded on the termination record, and this should be summarized in tabular fashion listing the proportion of patients discontinued and the recorded reason for discontinuation at the specific study stage listed above. Reasons for termination from the study as captured on the termination record are listed in Table 6. The number of patients whose data are missing, but the patient is not dropped from study; at each specific study stage should be indicated.

Table 4. Reasons for Study Termination

Reason for Study Termination	
Non-Evaluable	
No TMS treatment received	
No post-baseline assessments obtained	
Study Complete	
• Phase 1 complete (number of weeks of treatment)	
• Enrolled in Phase II	
Completed Phase II	
• Enrolled in Phase III	
Completed Phase III	
Study Not Complete (reason given)	
Satisfactory response – efficacy	
• Adverse event (specified on AE form)	
• Failed to return	
Unsatisfactory response – efficacy	
Patient request	
• Other (specified on termination record)	

Upon inspection of the proportion of reasons for discontinuation, a separate listing of the verbatim reasons categorized as 'Other' may be performed.

## Section 6. Summary of Study Treatments and Concomitant Therapy

## A. Motor Threshold Determinations and TMS Stimulation Parameters:

Motor threshold determination is determined prior to initiation of treatment in each study phase and at the beginning of each reintroduction treatment occurring in Phase III. Ad hoc motor threshold determinations may be repeated at any time if clinically indicated based on the opinion of the attending physician. Information for the baseline motor threshold determinations prior to each study phase or reintroduction treatment block, and any ad hoc motor threshold determinations will be summarized as part of the general summary of TMS treatment parameters as noted in Table 7.

44-02219-204, Rev C 21-JAN-2019

Table 5. Motor Threshold and TMS Treatment Session Summary Information
--

Variable	Туре	Items
Motor Threshold Determinations		
• Baseline Motor Threshold at each study phase (all patients)	Continuous	Mean, SD, Median, Range
• Proportion of patients with a post- baseline motor threshold at each study phase	Categorical	N, % of patients

 
Number of post-baseline motor thresholds obtained
 
	Categorical	Number of ad hoc MTs (per study phase)
	Continuous	Mean, SD, Median, Range (for each ad hoc MT)

## Section 7. Efficacy Analyses

## A. Efficacy Objectives:

The specific efficacy outcome variables, the time points of observation, and the data sets for analysis of these variables are summarized in Table 8. For each of the measures, the scoring conventions are shown in the Attachment at the end of this statistical plan. Statistical differences will be assessed between groups in phase I. Data analysis in phase II and III will be descriptive.

**NOTE**: The timing of assessment of the primary outcome measure is blinded to the investigator's and study team's view and is not specified in the protocol. This information is contained in the statistical plan summary document here, and should not be provided to any study personnel under any circumstances.

## **B.** Primary and Secondary Outcomes:

Table 6. Summary of Primary and Secondary Efficacy Study Measures, Prioritized Order of Analysis, and General Definitions of Outcome Measures

Primary Efficacy Outcome Measure	Definitions
HAMD24: total score, intent to treat	HAMD24 total score change from baseline value through
sample using last post-treatment score	week 6
Secondary Efficacy Outcome Measures	Definitions
Continuous outcomes HAMD17, HAMD24 (per protocol), MADRS, CDRS-R, QIDS-A17-R, CGI-S: total score, intent to treat sample using last post-treatment score	For each indicated measure, total score change from baseline value through week 6
Responder categorical outcome HAMD (24 and 17 Item versions) MADRS CDRS-R QIDS-A17-SR CGI-S	For HAMD, MADRS, CDRS-R, and QIDS-A17-SR: proportion of patient population achieving an end of acute phase total score reduction of $\geq$ 50% compared to baseline score
	For CGI-S: End of acute treatment score of 1, 2 or 3.
Factor scores derived from the HAMD including (using the last post-treatment value)	
Anxiety/Somatization	Anxiety/Somatization (sum of items 10, 11, 12, 13, 15, 17)
Core Factor	Core Factor (sum of items 1, 2, 3, 7, 8)
Maier	Maier (sum of items 1, 2, 7, 8, 9, 10)
Gibbons	Gibbons (sum of items 1, 2, 3, 7, 9, 10, 11, 14)
Retardation	Retardation (sum of items 1, 7, 8, 14)
Sleep	Sleep (sum of items 4, 5, 6)
Remitter categorical outcome	
HAMD (24 and 17 Item versions)	For HAMD24: End of acute treatment score < 11
MADDC	For HAMD17: End of acute treatment score < 8
MADRS	For MADRS: End of acute treatment score < 10
CDRS-R	For CDRS-R: End of acute treatment total score < 28
CGI-S	For CGI-S: End of acute treatment score 1 or 2

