The criteria above are clinically justified based on the results using the HAMD24 outcome measure in the prior adult studies which ranges from 1.7 to 2.5 (O'Reardon, et al, 2007; George, et al, 2010). The maximum Type I error rate of 15% for the adolescent data alone is justified given the large dataset available in adults (N=491) and that adult and adolescent populations should respond similarly to TMS Therapy. Simulations using data from the adult studies and N=100 adolescents, shows that with a type I error rate of 5%, the observed HAMD24 mean difference between active and sham treatment would need to be 2.67, which would require a result greater than what it would need to achieve had it been considered alone. For this reason, the 15% type I error rate for the adolescent data is justified.

If the criteria described above for pooling the adolescent study with the adult studies are not satisfied, the adolescent study must stand alone. If the results of the analysis of the adolescent study shows a statistically significant treatment group difference in favor of the active treatment at a pre-specified alpha level = 0.05, then this study alone will be sufficient to establish efficacy in the adolescent population.

A listing of the efficacy outcome measures and their intended sequence of testing in priority order are listed here. Note that the point of declaration of efficacy for the primary outcome measure is concealed from the Investigator and hence, is not specifically noted in this listing. All tests are to be performed on the intent to treat sample unless specifically noted. Please refer to the Schedule of Events for a listing of study timing for collection of primary and secondary outcome measures.

Primary Efficacy Outcome Measure	Definitions
HAMD24: total score, intent to treat	HAMD24 total score change from baseline value [Blinded
sample using last post-treatment score	point of declaration of efficacy for primary outcome
	measure included in statistical supplement]
Secondary Efficacy Outcome	
Measures	
Continuous outcomes	[Blinded point of declaration of efficacy for secondary
HAMD17, MADRS, CDRS-R, QIDS-	outcome measures included in statistical supplement]
A17-R, CGI-S: total score, intent to treat	
sample using last post-treatment score	
Responder categorical outcome	
HAMD (24 and 17 Item versions)	For HAMD, MADRS, CDRS-R, and QIDS-A17-SR:
MADRS	proportion of patient population achieving an end of acute

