CDRS-R	phase total score reduction of \geq 50% compared to baseline
QIDS-A17-SR	score
CGI-S	For CGI-S: End of acute treatment score of 1,2 or 3.
Factor scores derived from the HAMD	
including (using the last post-treatment	
value)	
Anxiety/Somatization	Anxiety/Somatization (sum of items 10, 11, 12, 13, 15, 17)
Core Factor	Core Factor (sum of items 1, 2, 3, 7, 8)
Maier	Maier (sum of items 1, 2, 7, 8, 9, 10)
Gibbons	Gibbons (sum of items 1, 2, 3, 7, 9, 10, 11, 14)
Retardation	Retardation (sum of items 1, 7, 8, 14)
Sleep	Sleep (sum of items 4, 5, 6)
Remitter categorical outcome	
HAMD (24 and 17 Item versions)	For HAMD24: End of acute treatment score < 11
MADRS	For HAMD17: End of acute treatment score < 8
CDRS-R	For MADRS: End of acute treatment score < 10
CGI-S	For CDRS-R: End of acute treatment total score < 28
	For CGI-S: End of acute treatment score 1 or 2

Table 4. Prioritized Order of Testing of Primary and Secondary Outcome Measures

1

The integrity of the masking of the efficacy treatment conditions will be evaluated by exploratory analyses of the efficacy measures with subjects grouped by prominent self-reported spontaneous adverse events. In addition, subjects and Parents will complete a Pre/Post-Treatment Expectations and Experience Questionnaire (PRE-TEEQ-A/PRE-TEEQ-P and POST-TEEQ-A/POST-TEEQ-P) that queries their initial expectations of trial outcome and final impression of the trial.

Neurocognitive safety outcome measures will be compared from end of each phase to Phase I baseline and previous phase completion assessments.

16 Safety and Adverse Events

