The null hypothesis will be tested in an analysis of covariance of the LV (value from 6-week visit unless it is missing, then LOCF used), using baseline score, and ATR medication resistance level as fixed effect covariates, adjusting for site differences using a random effect. As discussed elsewhere, the ATR medication resistance levels will group subjects categorically by number of medications which have shown an adequate degree of resistance for that subject. These resistance levels will be grouped into two categories in statistical model, 0-1 in the current episode or 2-4 in the current episode, unless the final distribution of ATR scores in the study population suggests another allocation would be more statistically appropriate. All tests are two-sided, at the 5% level. The primary outcome should be available and meaningful for nearly all subjects, so the main analysis will be by strict intention-to-treat as defined above. An analysis of observed cases only will be performed as a secondary outcome measure. A site by treatment interaction analysis will be done as a secondary analysis to see if there is significant heterogeneity in the effect of TMS across sites. In particular, we will examine site-specific treatment effects (with confidence intervals) to test for evidence of true reversal of effect.

Secondary outcomes include other continuous measures, and within-subject dichotomous variables as outlined in the efficacy variables described elsewhere in this protocol. The treatment effect null hypothesis will be tested by logistic regression on treatment group assignment with adjustment for site and ATR medication resistance level. In addition, the longitudinal symptom scores will be analyzed with a general linear model adjusting for baseline scores and ATR medication resistance level, using a saturated means model for time since baseline, with treatment effect parameterized by a linear effect in time. The correlation of scores within individuals over time will be handled by allowing a within-subjects residual covariance matrix selected by exploration of the sample semi-variogram, as described by Diggle, Liang and Zeger. If this exploration reveals that a mixed model approach will fit the covariance structure better, random effects will be included in the model. As in the main analysis, site by treatment interactions will be tested.

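### The secondary outcomes have a priority order but no stopping rule or gate on the primary, so 23 tests at two-sided 5% leave the family-wise error uncontrolled

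*SAP*

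**What the plan says.** The title of SAP Section 7.B, Table 6, opens "Summary of Primary and Secondary Efficacy Study Measures, Prioritized Order of Analysis". Protocol Section 15.2 introduces its counterpart with "A listing of the efficacy outcome measures and their intended sequence of testing in priority order are listed here" and titles it (Table 4) "Prioritized Order of Testing of Primary and Secondary Outcome Measures".

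On the level, SAP Section 2.B states "All tests are two-sided, at the 5% level", and protocol Section 15.2 has the same sentence. SAP Section 7.A says that group differences will be assessed statistically in Phase I, and Section 2.B specifies a logistic-regression test for the dichotomous outcomes. The secondary outcomes are therefore tested, not only summarised.

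SAP Section 2.D sets out the decision path for the primary: the adolescent study alone at 0.05 and, if that fails, the meta-analysis with three criteria. It does not mention secondary outcomes. Elsewhere the SAP does mark results as non-confirmatory: Phase II and III analyses are descriptive (7.A), any questionnaire p-values are for information (9.B), and HAMD suicidality changes are exploratory (9.C). Table 6 carries no such label.

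**The concern.** An order of testing protects against false positives only if an outcome's place in it has a consequence, such as that a failure earlier in the list closes the tests below it. Here no consequence is written. Followed literally, the plan lets the last remission outcome be called significant at 0.05 on the same terms as the first continuous outcome, whatever happened in between.

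The matter is sharpest when the stand-alone adolescent primary misses 0.05, because the plan then turns to a meta-analysis with adult data and is silent on the status of the adolescent secondary p-values. An isolated p<0.05 among them would have no stated standing, and a reader could not tell whether it was confirmatory.

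**Working it through.** **1. Count of secondary outcomes (SAP Table 6)**

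| Row | Outcomes | Number |
|---|---|---|
| Continuous | "HAMD17, HAMD24 (per protocol), MADRS, CDRS-R, QIDS-A17-R, CGI-S" | 6 |
| Responder | HAMD24, HAMD17, MADRS, CDRS-R, QIDS-A17-SR, CGI-S | 6 |
| HAMD factor scores | Anxiety/Somatization, Core, Maier, Gibbons, Retardation, Sleep | 6 |
| Remitter | HAMD24, HAMD17, MADRS, CDRS-R, CGI-S | 5 |

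Total: 6 + 6 + 6 + 5 = 23. Protocol Table 4 omits HAMD24 (per protocol), giving 5 + 6 + 6 + 5 = 22. The count leaves out the observed-case, longitudinal and other per-protocol analyses.

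**2. The plan's own figure**

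The documents state no family-wise error for the secondary outcomes, only 5% per test, so there is no figure to reproduce.

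**3. No true effect on any outcome, independent tests**

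- Expected number of p<0.05: 23 × 0.05 = 1.15, which holds at any correlation.
- At least one: 1 − 0.95^23 = 0.693. For the protocol's 22: 1 − 0.95^22 = 0.676.
- At least one in favour of active: 1 − 0.975^23 = 0.441.

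**4. Correlated tests**

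The documents give no correlations, so a common correlation ρ is assumed and varied. Each statistic is Z_i = √ρ·U + √(1−ρ)·E_i, with U and E_i independent standard normal and i = 1 to 23. A result counts as significant if |Z_i| > 1.96, or if Z_i > 1.96 for results favouring active. There were 400,000 simulated draws for each ρ.

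| ρ | At least one p<0.05 | At least one favouring active |
|---|---|---|
| 0 | 69% | 44% |
| 0.3 | 58% | 30% |
| 0.5 | 45% | 23% |
| 0.7 | 31% | 15% |
| 0.8 | 23% | 12% |
| 0.9 | 16% | 8% |

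The two-sided figure falls below 50% at about ρ = 0.4. Interpolating between 0.3 and 0.5: 0.3 + 0.2 × (0.582 − 0.500)/(0.582 − 0.448) = 0.42.

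**5. How often the stand-alone primary could miss**

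Inputs from SAP Section 2.A: 50 per arm, effect size 0.50 to 0.60, two-sided 0.05. Power ≈ Φ(d√(n/2) − 1.96).

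- d = 0.50: Φ(2.50 − 1.96) = 0.705, so the miss rate is about 29%.
- d = 0.60: Φ(3.00 − 1.96) = 0.851, so the miss rate is about 15%.

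The situation in which the status of the secondary p-values is unclear is therefore a realistic one, even if the assumed effect is true.

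**6. What a gated fixed sequence would do**

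Each step uses the full 5%, and a step is reached only if all earlier steps were significant. A false rejection anywhere requires rejecting the first true null hypothesis in the order, which has probability at most 0.05. This bound holds at any correlation. For comparison, Bonferroni over 23 tests would require 0.05/23 = 0.0022 for each.

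**The case against.** The strongest reply is that a fixed sequence was meant. Such a procedure tests every step at the full two-sided 5%, so a 5% level per test fits it, and the protocol's words "intended sequence of testing in priority order are listed here" point that way. A reader might infer that the plan deliberately ignores its own order, or that it applies 5% to every secondary test whether or not the primary succeeds. The documents do not support either reading. The sentence setting the level sits in the paragraph on the primary covariance analysis. It also cannot govern every test in the plan, since Section 2.D uses 0.10 for the interaction and 15% for one adolescent criterion. This part of the reply stands. What remains is that an intended sequence cannot be run from the text: the stop and the gate are not written, several outcomes share each row, and the two lists differ by one outcome.

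The second reply is that the outcomes overlap heavily. HAMD17 and the six factor scores are built from items of HAMD24 (SAP Attachment 1), and HAMD response and remission are cut-points on the same totals. A reader might infer from the independence figure that a false positive is more likely than not. That requires a correlation below about 0.4, and for results favouring active the chance stays below 50% even under independence. This stands, and it is why the size is given as a range.

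The third reply is that efficacy is defined only on HAMD24. That is correct. A reader might infer that the plan lets a secondary outcome rescue a failed primary, but no passage does so. The point concerns the standing of secondary p-values, not the primary conclusion.

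One caution: a figure at the end of SAP Section 2.C could not be read. If it contains a rule for the secondary outcomes, this point would need another look.

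**Conclusion.** The priority order has no written effect on inference, and the readable text of both documents leaves the family-wise error of the secondary outcomes uncontrolled. With no true effect, the chance of at least one nominal finding is 69% under independence and about 16% to 45% at correlations of 0.9 to 0.5, roughly three to nine times the 5% applied to each test. For findings favouring active it is about 8% to 23% over the same range. These figures rest on 23 tests, no effect on any of them, and an assumed common correlation. The true pattern is not given and will not be uniform. The primary analysis is unaffected. This is a cheap improvement, worth making because the order needed for it is largely written already.

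**What to change.** Add to SAP Section 7.B, and align protocol Section 15.2:

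- Number the outcomes within each row of Table 6, so that there is one order from first to last.
- State which per-protocol population HAMD24 (per protocol) uses. SAP Section 3.C defines two, naming the second as the main one while also requiring analyses in the first. Make the protocol list match.
- Test in that order at two-sided 5%, starting only if the stand-alone adolescent HAMD24 analysis is significant at 0.05. Stop at the first p of 0.05 or more and treat everything after it as descriptive.
- Treat all secondary p-values as descriptive if the stand-alone primary fails, including when success comes only through the adult meta-analysis. That route accepts an adolescent error rate of up to 15%, so letting it open the sequence would lose the 5% bound.

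This holds the family-wise error for the stand-alone primary and the secondary outcomes together at 5% or less. It does not cover the meta-analysis route itself.

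The cost is a few sentences, with no added patients, visits or data. The downside is fewer formal secondary claims: remission comes last, so one early miss makes it descriptive. If the sponsor does not want that, labelling all secondary p-values descriptive is simpler and also resolves the point.
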